8.1.2.1. Analysis of Primary Endpoint

DLT is a primary endpoint of the study. The properties of the statistical methods for the analyses of DLTs are described in Section 4. Adverse events constituting DLTs are detailed in Section 3.2 of the study protocol. Adverse events and adverse events constituting DLTs will be listed per dose level (ie, by cohort). A binary variable will be created at the patient level to indicate whether or not a patient has experienced any of the adverse events that are considered DLT. If required, a summary table will be created by cohort to present number and percentage of patients experiencing DLT and each specific adverse event constituting DLT.

Adverse Events (AEs) will be graded by the investigator according to the CTCAE version 4.03 and coded using the Medical Dictionary for Regulatory Activities (MedDRA). The focus of AE summaries will be on Treatment Emergent Adverse Events, those with initial onset or increasing in severity after the first dose of study treatment and before the start of any new anti-cancer systemic therapy. The number and percentage of patients who experienced any AE, SAE, treatment related AE, and treatment related SAE will be summarized. The summaries will present AEs both on the entire study period by dose (i.e., by cohort) and by cycle. The number and percentage of patients who discontinued from study medications due to AE or discontinued from the study due to AEs will also be presented.

AE, SAE, treatment related AE, treatment related SAE will be presented by system organ class and preferred term for each cohort. Severity summary tables will also be presented where AE, SAE, treatment related AE, and treatment related SAE will be presented for each cohort by system organ class and preferred term according to the worst toxicity grade.

Treatment related AE in this study refers to those adverse events that are determined by investigator as related to either adenovirus, or plasmid DNA, or tremelimumab, or PF-06801591. If deemed necessary, further summary of component-related AE may be presented.

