### **1.3. Overview of PrCa VBIR Regimen (PF-06753512)**

An effective anti-tumor immune response should involve the activation of specific effector T cells and/or the production of functional anti-tumor antibodies targeted against antigens that are highly expressed by the patients' tumor. In this study, two antigen-delivery systems will be used in a heterologous prime/boost approach to elicit immune responses to several selected prostate cancer antigens. As these are self-antigens, the antigen delivery systems were selected to break immune tolerance and to elicit high T cell titers. The approach makes use of concomitant administration of immune modulators to drive immune response expansion as well as condition the immune suppressive tumor micro-environment to allow sustained immune-mediated killing of tumor cells.

The initial PrCa VBIR regimen for prostate cancer (PF-06753512) consisted of three basic components described below. A fourth component (described below) has now been added to the PrCa VBIR regimen, which is the anti-PD-1 antibody PF-06801591:

1. A priming immunization with a replication-deficient adenovirus (AdC68) vector, derived from a chimpanzee-specific AdC68 that expresses three selected prostate cancer-specific antigens, administered intramuscularly (IM).
2. Plasmid deoxyribonucleic acid (DNA) booster vaccinations, encoding the same antigens, administered IM with an electroporation device (intramuscular TriGrid Delivery System (TDS-IM)).
3. Low dose anti-cytotoxic T lymphocyte-associated antigen 4 (CTLA4) monoclonal antibody (tremelimumab) delivered subcutaneously (SC) in conjunction with each immunization at a site as close as possible to the vaccine vector delivery site. The anti-CTLA4 administration is aimed at enhancing the vector-elicited immune response by blocking a natural mechanism for limiting antigen-specific T cell expansion.
4. In addition to the 3 agents described above, PF-06801591 will be added to treatment with PrCa VBIR. PF-06801591 is a humanized, hinge region-stabilized IgG4 monoclonal antibody (mAb) specific for human PD-1. This antibody can selectively and reversibly bind to human PD-1 and block the interaction between PD-1 and PD-L1/programmed death-ligand 2 (PD-L2). The administration of PF-06801591 will help maintain the PrCa VBIR-induced T cell response over time, by blocking the inhibitory effects against T-cells, which result from tumor-activated PD-1/programmed death-ligand 1 (PD-L1).

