#### **5.7.3. Participants on beta blockers**

Per the TDS-IM Investigator's Brochure (28-Jun-2019), two cases of syncope have been reported in association with the device in a total of over 800 subjects receiving up to 5 administrations. Caution should be undertaken during injections in participant taking beta blockers. Strong consideration should be given to placing the participant in prone position depending on the participant's medical condition.

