## **8.3. Definition of an Adverse Event**

An AE is any untoward medical occurrence in a clinical investigation patient administered a product or medical device; the event need not necessarily have a causal relationship with the treatment or usage. Examples of AEs include but are not limited to:

- Abnormal test findings;
- Clinically significant symptoms and signs;
- Changes in physical examination findings;
- Hypersensitivity;
- Drug abuse;
- Drug dependency.

Additionally, they may include the signs or symptoms resulting from:

- Drug overdose;

- Drug withdrawal;
- Drug misuse;
- Drug interactions;
- Extravasations;
- Exposure during pregnancy (EDP);
- Exposure via breastfeeding;
- Medication error;
- Occupational exposure;
- Worsening of signs and symptoms of the malignancy under study should be reported as AEs in the appropriate section of the CRF. Disease progression assessed by measurement of malignant lesions on radiographs or other methods should not be reported as AEs.

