## 8.9. Causality Assessment

The investigator's assessment of causality must be provided for all AEs (serious and non-serious); the investigator must record the causal relationship in the CRF, as appropriate, and report such an assessment in accordance with the SAE reporting requirements if applicable. An investigator's causality assessment is the determination of whether there exists a reasonable possibility that the investigational product caused or contributed to an AE; generally the facts (evidence) or arguments to suggest a causal relationship should be provided. If the investigator does not know whether or not the investigational product caused the event, then the event will be handled as "related to investigational product" for reporting purposes, as defined by the sponsor (see the section on [Reporting Requirements](#)). If the investigator's causality assessment is "unknown but not related to investigational product," this should be clearly documented on study records.

In addition, if the investigator determines that an SAE is associated with study procedures, the investigator must record this causal relationship in the source documents and CRF, as appropriate, and report such an assessment in accordance with the SAE reporting requirements, if applicable.

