2.1. Study Design

This is a Phase 1, open label, multi-center, multiple dose, safety, PK, PD and immunogenicity study evaluating the components of a vaccine-based immunotherapy regimen for prostate cancer (PrCa VBIR). PrCa VBIR consists of the following components: Adenovirus (AdC68), pDNA and tremelimumab. In addition, cohorts will evaluate PrCa VBIR when given in combination with PF-06801591.

The study will enroll patients with the following stages of prostate cancer: patients with asymptomatic/minimally symptomatic metastatic castration-resistant prostate cancer (mCPRC) who have not received secondary hormones (M1 pre-secondary hormones), patients with rising PSA at high risk for recurrence (biochemically relapsed), and asymptomatic/minimally symptomatic mCPRC patients for whom secondary hormone treatment failed (M1 post-secondary hormones). The study is divided in to two parts, Dose Escalation (Part A) followed by Dose Expansion (Part B).

The overall study design is presented in Figure 1.

Figure 1. Overall Study Design

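### The SAP's definition of a treatment-related AE omits the TDS-IM electroporation device and procedure, so events attributed solely to them are left out of the treatment-related AE and SAE tables

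*SAP*

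**What the plan says.** SAP 8.1.2.1 defines a treatment-related AE as one "determined by investigator as related to either adenovirus, or plasmid DNA, or tremelimumab, or PF-06801591". That definition feeds several tables: "The number and percentage of patients who experienced any AE, SAE, treatment related AE, and treatment related SAE will be summarized", followed by tables by system organ class, preferred term and worst grade for each cohort. One further breakdown is mentioned and it is optional: "If deemed necessary, further summary of component-related AE may be presented". SAP 2.1 says what a component is: "PrCa VBIR consists of the following components: Adenovirus (AdC68), pDNA and tremelimumab". The device is not among them. The SAP text has no device-related or procedure-related AE category and no summary of device complaints.

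The protocol gives the device more weight:
- Section 1.3 describes the plasmid boosters as "administered IM with an electroporation device (intramuscular TriGrid Delivery System (TDS-IM" (the TDS-IM device).
- Section 1.6.4.1 (at its end) assigns the device its own reference safety document.
- Section 5.6 names the device separately from investigational product.
- Section 5.7.3 reports that "two cases of syncope have been reported in association with the device in a total of over 800 subjects receiving up to 5 administrations".
- Section 8.3 states that "An AE is any untoward medical occurrence in a clinical investigation patient administered a product or medical device".
- Section 8.9 requires that "if the investigator determines that an SAE is associated with study procedures, the investigator must record this causal relationship", in the source documents and CRF.
- Section 8.14.3 collects all device complaints on the CRF, and Section 8.6 notes that a complaint may meet SAE criteria.

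**The concern.** The regimen cannot be given without electroporation, so a reader of the treatment-related tables will take them to cover everything the study administers. Under the SAP rule they do not. An event judged to come from the electroporation alone, with no contribution from the plasmid, is classed as not treatment related. The protocol collects some of the information needed to identify such events, but the SAP gives it no place in any related-event table. What is at stake is the completeness of the treatment-related AE and SAE tables, and the visibility of any device signal in them.

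**Working it through.** No design figure is involved: SAP 4.1 plans no hypothesis test, and the safety analysis is descriptive. The check sets the rule against the rest of the text and then gauges scale.

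**1. Does the rule exclude device-only events?** Yes. The list is closed at four products, and the optional breakdown is by component, which does not include the device.

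**2. Where do such events still appear?**
- In the all-causality AE and SAE tables of SAP 8.1.2.1, by cohort, system organ class, preferred term and worst grade.
- In the primary endpoint (SAP 6.1 and 6.4), which is treatment-emergent AEs whatever the cause.
- As a DLT in principle, since Protocol 3.2 excludes by cause only events related to disease or progression. In practice the DLT window is the first 28 days after the first AdC68 dose, and the first electroporation is scheduled for Day 29 (±2 days), so the overlap is marginal.

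**3. Does another planned analysis isolate them?** No.
- Every cycle includes plasmid by electroporation (Protocol 3.1), so no cohort is free of the device.
- The Day 1–28 versus Day 29–85 split in SAP 8.1.2.2 separates the time before electroporation from the time with it, but it cannot separate plasmid from device.
- Within related-event reporting, investigator attribution is the only route, and the definition does not use it for the device.

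**4. Exposure.** 3 plasmid days per cycle × 2 cycles = 6 electroporation days. Given bilaterally (Protocol 5.4), 6 × 2 = 12 electroporations before maintenance, where plasmid continues every 2 months.

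**5. Effect of one reclassified participant** (100/n percentage points):

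| Cohort | n | Shift |
|---|---|---|
| 5B | 15 | 6.7 |
| 3B | 18 | 5.6 |
| 1B | 20 | 5.0 |

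**6. Illustration on a reported event.** Protocol 1.3.2 gives treatment-related injection site pain in 8 of 69 participants: 8/69 = 11.6%, which reproduces the protocol's figure. Let s be the share attributed to the device only. The documents give no value for s, so it is assumed over its full range. The related rate is 8(1 − s)/69:

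| s | Related rate |
|---|---|
| 0% | 11.6% |
| 25% | 6/69 = 8.7% |
| 50% | 4/69 = 5.8% |
| 100% | 0% |

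**7. Known device event.** Syncope: 2/800 = 0.25%, an upper figure because the denominator is over 800. Taking this as a per-participant rate, P(at least one case) = 1 − (1 − 0.0025)^n. For the 20 + 18 + 15 = 53 Part B participants this is 12.4%; for 69 participants it is 15.9%.

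**The case against.** The strongest reply is that the SAP does not contradict the protocol and the consequence is narrow. Protocol 9.5.1 uses treatment related without defining it, and Protocol 8.9 frames causality around investigational product, which is what the SAP lists. Only an event attributed solely to the device or procedure drops out. Plasmid and device share one procedure and one site, the causality test includes contribution as well as cause, and unknown causality is handled as related for reporting. An investigator may therefore naturally code such an event to plasmid DNA. The only relevant data point that way: injection site pain (8/69) and injection site discomfort (5/69 = 7.2%) were reported as treatment related.

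Most of this stands as a limit on size. It does not restore the missing category. The protocol asks separately about procedure causality for SAEs, so the sole-attribution case is one it foresees, and for that case the SAP rule gives the answer not related.

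Stronger readings that a reader might infer are not supported:
- **That the primary endpoint is biased.** It is all-causality and loses nothing.
- **That device events disappear from the reporting.** They remain in the all-AE and all-SAE tables; only the related-event tables omit them.
- **That the RP2D is affected.** Protocol 3.5 rests it on the totality of clinical evidence and does not mention treatment-related rates.
- **That injection site events will move to unrelated.** No such case is documented.
- **That 12 electroporations against a record of up to 5 administrations measures the excess exposure.** The documents do not say whether an administration is a site or a visit; by visit the comparison is 6 against 5.

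**Conclusion.** The point holds as a defect in one definition. As written, SAP 8.1.2.1 classes an AE or SAE attributed solely to the TDS-IM device or procedure as not treatment related, and no other related-event summary in the SAP captures it. Any error can only be an understatement of the treatment-related rates. Its size is unknown: it could be zero if investigators attribute all such events at least partly to plasmid DNA, and one participant is worth 5.0 to 6.7 points in a Part B cohort. The 0% to 11.6% range for injection site pain shows sensitivity to an assumed share and is not an estimate. The conclusion assumes that at least some investigators attribute events to the device alone. The documents do not show whether the CRF has a device causality field for non-serious AEs. The all-causality primary endpoint and the all-AE and all-SAE tables stand as planned.

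**What to change.** Before database release, do one of the following in SAP 8.1.2.1:
- Extend the definition to events related to *adenovirus, plasmid DNA, tremelimumab, PF-06801591, or the TDS-IM device/administration procedure*; or
- Keep the four-product definition and add a separate table of device- or procedure-related AEs and SAEs by cohort.

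In either case, add a listing of device complaints with any linked AEs. Use the SAE procedure causality already recorded under Protocol 8.9. Check whether the CRF captured device attribution for non-serious AEs, and state as a limitation that this attribution is available only where it did.

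The cost is a wording change, one table or extended definition, and one listing. Some data queries may be needed, and related-event rates may rise slightly.

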8.1.2.2. Analysis of Secondary Safety Endpoints

These safety endpoints will be analyzed according to the Pfizer Data Standard. To better characterize the safety profile of the different regimen components analyses of safety will be conducted by cohort, by cycle (i.e., Cycle 1,2, maintenance cycle) and by period (Day 1 to Day 28, Day 29 to Day 85).

Laboratory Tests Abnormalities

The number and percentage of patients who experienced laboratory test abnormalities will be summarized according to worst toxicity grade observed for each lab assay. The analyses will summarize laboratory tests by cohort and visit. The most recent measurement prior to dosing is considered as baseline.

For laboratory tests without CTCAE grade definitions, results will be categorized as normal, abnormal or not done.

ECG

The analysis of ECG results will be based on patients in the safety analysis set with baseline and on-treatment ECG data. Baseline is defined as the pre-dose ECG collected before the first dose of any component of the study treatment.

ECG measurements (an average of the triplicate measurements) will be used for the statistical analysis and all data presentations. Any data obtained from ECGs repeated for safety reasons after the nominal time-points will not be averaged along with the preceding triplicates. Interval measurements from repeated ECGs will be included in the outlier analysis (categorical analysis) as individual values obtained at unscheduled time points.

QT intervals will be corrected for heart rate (QTc) using standard correction factors (ie, Frederica's). Data will be summarized and listed for QT, HR, PR, QRS, and QTcF by cohort. Individual QT intervals will be listed by time and cohort. Descriptive statistics (n, mean, median, standard deviation, minimum, and maximum) will be used to summarize the absolute corrected QT interval and changes from baseline in corrected QT after treatment by cohort and time point. For each patient and by treatment, the maximum change from baseline will be calculated as well as the maximum post-baseline interval across time-points. Categorical analysis will be conducted for the maximum change from baseline in corrected QT and the maximum post-baseline QT interval.

Shift tables will be provided for baseline vs worst on treatment corrected QT.

If applicable, the effect of relevant drug concentrations on corrected QT change from baseline will be explored graphically. Additional concentration-corrected QT analyses may be performed. Data may be pooled with other study results and/or explored further with PK/PD models.

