12. **Coagulation:** Should include Prothrombin Time (PT) or International Normalized Ratio (INR) and Partial Thromboplastin Time (PTT). Samples will be analyzed locally.
13. **Cardiac Troponin:** For participants undergoing screening, circulating levels of cardiac Troponin-I (cTnI) must be measured and found to be within the normal reference range within 28 days before study entry, preferably using the central laboratory kits provided. See [Section 7.1.7](#) for full details.
14. **Urinalysis:** Dipstick is acceptable. Microscopic analyses if dipstick abnormal. Samples will be analyzed locally.
15. **Triplicate 12 leads ECGs:** At each time point, three consecutive 12-lead ECGs will be performed approximately 2 minutes apart to determine mean QTcF interval. If the mean QTcF is prolonged (>500 msec), the ECGs should be re-evaluated by a qualified person at the institution for confirmation. Additional triplicate ECGs may be performed as clinically indicated.
16. **Registration:** Participant number and dose level allocation operated by Pfizer Inc.
17. **Investigational Product Administration:** Treatment to be administered after all other assessments required on that day have been performed.
18. **Tumor Assessments:** Tumor assessments will include all known or suspected disease sites. Screening images may be obtained within 5 weeks of registration. Imaging obtained as part of standard of care but within 28 days (-7 days) of registration may be used for screening assessment. Imaging may include chest, abdomen and pelvis CT or MRI scans or bone scans. Bone scans will be performed at baseline if disease is suspected and on-study as appropriate to follow disease. Baseline central nervous system (CNS) imaging is not required with the exception of symptomatic participants to rule out CNS metastases. CT or MRI scans, as well as bone scans, when indicated, are to be done every 8 weeks ( $\pm$  5 days) with the first one to occur 8 weeks after C1D1 until disease progression that requires new treatment modality, permanent discontinuation, or death. Disease progression will be confirmed with two consecutive timepoints at least 4-6 weeks apart in the absence of rapid clinical deterioration. Tumor assessment should be repeated at the End of Treatment visit if more than 6 weeks have passed since the last evaluation. **CCI** [REDACTED]  
[REDACTED]  
[REDACTED]

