## Schedule of Study Treatment, Pharmacokinetics, and Immunogenicity Assessments – Expansion Cohorts, 3B and 5B

Protocol Activity	Screen (≤28 days)	Treatment Period											End of Treatment	Post Treatment					
		Cycle 1						Cycle 2						Follow- Up (Months after EOT visit)					
Study Day		Day 1	Day 8	Day 15	Day 22	Day 29	Day 43	Day 57	Day 71	Day 85	Day 113			M1	M2	M4	M6		
Cycle Day											Day 1	Day 29	Day 57	Day 85	Day 99		28-35 days		
Visit Window (hours)		±24 hr	±48 hr	±48 hr															
Visit Window (days)					±2	±4	±2	±4	±2	±2	±2	±2	±2	±2	±4		±4	±4	±4
Study Treatment																			
Adenovirus 		X									X								
Plasmid DNA 					X		X		X		X	X	X						
Tremelimumab 		X			X		X		X		X	X	X	X					
PF-06801591 		X			X		X		X		X	X	X	X					
Pharmacokinetics and Tremelimumab Immunogenicity																			
PK for tremelimumab 		X			X		X		X	X	X				X		X	X	X
ADA for tremelimumab 		X			X				X		X				X		X	X	X
PK for PF-06801591 		X			X		X		X	X	X				X		X	X	X
ADA for PF-06801591 		X			X				X		X				X		X	X	X

Abbreviations: ADA = Anti-drug antibody.

1. Adenovirus will be administered intramuscularly on Day 1 of each cycle. Tremelimumab and PF-06801591 will be administered after the adenovirus. Both adenovirus injections should be administered prior to administering the tremelimumab and PF-06801591.
2. Plasmid DNA vaccinations will be administered intramuscularly using an electroporation device on Day 29, Day 57 and Day 85 of each cycle. Tremelimumab and PF-06801591 will be administered after the plasmid DNA. Both pDNA vaccinations should be administered prior to administering the tremelimumab and PF-06801591.
3. Tremelimumab will be administered subcutaneously in close proximity to the vaccine injected muscle and vaccine draining lymph nodes on Day 1, Day 29, Day 57 and Day 85 of each cycle. Tremelimumab will be administered after the adenovirus or plasmid DNA and before the PF-06801591. Both tremelimumab injections should be administered prior to administering the PF-06801591.
4. PF-06801591 will be administered subcutaneously in close proximity to the vaccine injected muscle and vaccine draining lymph nodes on Day 1, Day 29, Day 57 and Day 85 of each cycle. PF-06801591 will be administered after the adenovirus or plasmid DNA and after the tremelimumab.

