#### **5.4.2. Dosing Interruptions/Delays**

Participants experiencing Grade 3 or 4 potentially treatment related toxicity or intolerable Grade 2 toxicity despite supportive care should have their treatment with all of the components interrupted/delayed. Appropriate follow-up assessments should be done until adequate recovery occurs as assessed by the investigator.

Re-treatment following treatment interruption for treatment related toxicity may not occur until all of the following parameters have been met:

- ANC  $\geq 1,000/\text{mm}^3$ .
- Platelets count  $\geq 50,000/\text{mm}^3$ .

- Non-hematologic toxicities have returned to baseline or Grade  $\leq 1$  severity (or, at the investigator discretion, Grade  $\leq 2$  if not considered a safety risk for the patient).

If a treatment delay results from worsening of hematologic or biochemical parameters, the frequency of relevant blood tests should be increased as clinically indicated. If these conditions are met within 2 weeks of treatment interruption or cycle delay, investigational product(s) may be resumed. Refer to [Section 5.4.4](#) for adverse events requiring dose reduction at the time of treatment resumption.

If these parameters have not been met after 2 weeks of dosing interruption or 2 weeks of new cycle delay, permanent discontinuation of treatment should be considered. Treatment resumption for participants recovering from treatment-related toxicity after  $>2$  weeks of treatment interruption or cycle delay may be considered only if the participant is deemed to be deriving obvious clinical benefit per the investigator's best medical judgment and needs to be agreed between the investigator and the sponsor.

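### The Day 28/29 line in the by-period safety summaries counts pre-plasmid Day 29 laboratory samples, and events around a shifted first plasmid dose, in the wrong vaccine phase

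*SAP*

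**What the plan says.** SAP 8.1.2.2 gives the purpose of its safety cuts as "To better characterize the safety profile of the different regimen components". It then asks for analyses by cohort, "by cycle (i.e., Cycle 1,2, maintenance cycle", and "by period (Day 1 to Day 28, Day 29 to Day 85". Only the period cut has day limits. The laboratory paragraph of the same section summarizes abnormalities by worst toxicity grade and tabulates by cohort and visit. Neither document says which period or cycle receives a sample taken on a dosing day before the dose.

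The protocol's treatment schedule for Cohorts 3B and 5B states "Adenovirus will be administered intramuscularly on Day 1 of each cycle" and "Plasmid DNA vaccinations will be administered intramuscularly using an electroporation device on Day 29, Day 57 and Day 85 of each cycle". The antibodies in those cohorts are given "on Day 1, Day 29, Day 57 and Day 85 of each cycle". The Schedule of Activities footnote on investigational product administration states "Treatment to be administered after all other assessments required on that day have been performed". The Day 29 visit has a ±2-day window, counted from the previous dosing visit. Dosing can also be held for toxicity. Protocol 5.4.2 says "If these conditions are met within 2 weeks of treatment interruption or cycle delay, investigational product(s) may be resumed", and allows later resumption in restricted circumstances.

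**The concern.** The period cut is useful only if its boundary coincides with the change of vaccine component. The change happens when the first plasmid dose is given, not at midnight before Day 29. A calendar line therefore fails in two ways.

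- A laboratory abnormality found in the Day 29 pre-dose sample can reflect only what was given on Day 1, but it is tabulated with the plasmid phase.
- If the first plasmid dose is early or late, events with onset dates near the boundary are also placed on the wrong side. Toxicity holds make this worse, because the participants whose dose is held are those who already have toxicity.

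What is at stake is the comparison for which the cut was created. Protocol 2.3 lists laboratory abnormalities among the Part B primary endpoints, so these are not minor data. Troponin shows the problem clearly. Under Protocol 7.1.7 the first scheduled on-treatment result is for the Day 29 dose and may be taken up to 10 days before it. The same pre-plasmid test counts in the first period if drawn before Day 29 and in the second if drawn on Day 29.

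**Working it through.** The plan states no figure to reproduce, and no power or error-rate calculation applies. The check compares the dosing calendar with the SAP cut.

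**Inputs.** AdC68 on Day 1 and plasmid DNA on Days 29, 57 and 85 of each cycle (protocol treatment schedules). Assessments before dosing (Schedule of Activities footnote). Cycle 1 hematology and chemistry after Day 1 on Days 8, 15, 22, 29, 43, 57, 71 and 85 (Schedule of Activities). Periods Day 1 to 28 and Day 29 to 85 (SAP 8.1.2.2).

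**1. Calendar.** A cycle is 16 weeks, so Cycle 2 Day 1 is 16 × 7 + 1 = Day 113. This agrees with SAP 5.6.

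**2. Each Cycle 1 draw against the cut.**

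| Draw | Last vaccine before the sample | Period under the SAP cut |
|---|---|---|
| Day 8 | AdC68 | Day 1–28 |
| Day 15 | AdC68 | Day 1–28 |
| Day 22 | AdC68 | Day 1–28 |
| **Day 29** | **AdC68** | **Day 29–85** |
| Days 43, 57, 71, 85 | plasmid DNA | Day 29–85 |

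**3. Shares of scheduled draws.** Four draws follow AdC68 and precede plasmid DNA, and one is misplaced: 1/4 = 25%. Five draws lie in Day 29 to 85, and one precedes any plasmid DNA: 1/5 = 20%.

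**4. Visit window.** 29 − 2 = 27 and 29 + 2 = 31, so the visit may fall on Days 27 to 31. With a dose on Day 27 or 28, post-plasmid events up to the end of Day 28 count in the first period. With a dose on Day 30 or 31, one or two whole pre-plasmid days (from Day 29) and the pre-dose sample count in the second.

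**5. Held dose.** If the first plasmid dose moves by 14 days to Day 43, Days 29 to 42 precede plasmid DNA but are counted in the plasmid period: 42 − 29 + 1 = 14 days.

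**6. Cycle 2 Day 1.** This sample (Day 113) follows the plasmid dose of Day 85. By study day it lies in neither period. By cycle it enters Cycle 2, which opens with AdC68. The SAP does not say whether the period limits are study days or cycle days. The two coincide in Cycle 1, so steps 2 to 5 are unaffected.

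**7. Remainder of Cycle 1.** Days 86 to 112, which are 112 − 86 + 1 = 27 days after the third plasmid dose, lie in neither period.

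**The case against.** The strongest reply is that the laboratory paragraph tabulates by visit. Day 29 then appears on its own row, and a reader can recognize it as pre-plasmid. This stands as a limit on the damage: by-visit tables are unaffected. It does not rescue the by-period summaries, because the same section asks for analyses of safety by period and for worst grades, and a worst grade taken over Day 29 to 85 includes the Day 29 sample.

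Second, the section defers to the sponsor's data standard, which may contain a rule for same-day pre-dose samples. That standard is not in the documents, so such a rule cannot be excluded. The day limits that are written give the wrong assignment when followed literally.

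Third, Day 1 to 28 mirrors the 28-day DLT window of Protocol 3.2, and the study is descriptive with no hypothesis tests. Both are true. But Day 29 is 29 − 1 = 28 days after the first AdC68 dose, so the Day 29 pre-dose draw is the natural laboratory check at the end of that window.

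Fourth, adverse events carry onset dates, so the pre-dose-sample argument does not apply to them. That is correct: they are affected only through the visit window and held doses.

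Fifth, the cut cannot isolate AdC68 in most cohorts. From Cohort 3A on, tremelimumab is given on Day 1 and on every plasmid day, and so is PF-06801591 in Cohorts 6A to 9A, 3B and 5B. Only Cohorts 1A and 2A (7 participants, Protocol 1.3.2) received vaccine alone. This stands, and no redefinition of periods changes it.

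**Conclusion.** The point holds for the period cut. Followed literally, SAP 8.1.2.2 assigns one of the four post-AdC68, pre-plasmid hematology and chemistry draws to the plasmid period, where it is one of five. Window shifts move up to about two days of events in either direction, and a two-week hold adds 14 days of pre-plasmid time to the plasmid period. The draw counts assume visits on their scheduled days. The documents do not say how often doses are shifted or held.

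A reader might infer more than the documents support:

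- **That a quarter of AdC68-phase abnormalities are misplaced.** The 25% is a share of scheduled draws. Reading it as a share of abnormalities needs an assumption such as uniform onset over the 28 days, and the documents give no onset pattern. The true share first seen on Day 29 could lie anywhere from none to all.
- **That Cycle 2 Day 1 shows the same error.** It runs the other way: plasmid-phase findings would enter the cycle that opens with AdC68.
- **That the by-cycle cut also uses fixed days.** It has no day limits. It lacks an assignment rule.
- **That this is the only planned component-level table.** SAP 8.1.2.1 also permits component-related adverse event summaries, based on investigator attribution, if deemed necessary.

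The defect is modest, but it falls on the contrast that the cut is meant to show. It should be corrected before the tables are programmed.

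**What to change.** In SAP 8.1.2.2, replace the fixed days with periods anchored to actual dosing:

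- **First period:** from the first AdC68 dose until just before the first plasmid-DNA dose, including same-day pre-dose assessments.
- **Plasmid period:** from that dose until just before the Cycle 2 AdC68 dose, or until the end of Cycle 1 follow-up if there is no Cycle 2. The end point is needed so that the Day 113 AdC68 dose and what follows it are not absorbed. It also covers Days 86 to 112.
- **By-cycle summaries:** assign Cycle 2 Day 1 pre-dose samples to Cycle 1.
- **Labels:** state that, from Cohort 3A on, the first period reflects AdC68 plus tremelimumab, and PF-06801591 where assigned.

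The cost is SAP wording and programming on dosing and assessment dates already collected. Nothing changes in treatment or visits. The one drawback is that period lengths will differ between participants, so person-time should be reported beside the counts. Adverse events that start on a dosing day with no onset time will need a stated convention.
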